## 16.1.5. Sensitivity Analysis of Primary Efficacy Variable(s)

The sensitivity analyses will be conducted similar to the primary efficacy analysis including the paired t-test using the PP population.

## 16.2. Secondary Efficacy

Secondary efficacy variables will be analyzed using both the mITT as well as the PP population.

## 16.2.1. Secondary Efficacy Variables & Derivations

Change in mean sitting SBP and DBP between Visit 2 (Week 0) and Visit 4 (Week 8).

Page 29 of 46

• Change in mean sitting DBP and SBP

Change in mean sitting SBP and DBP between Visit 2 (Week 0) and Visit 3 (Week 4).

• Change in mean sitting DBP and SBP

Change in mean sitting DBP between Visit 2 (Week 0) and Visit 5 (Week 12). Change in mean sitting DBP and SBP between Visit 3 (Week 4), Visit 4 (Week 8) and Visit 5 (Week 12) in patients under extemporaneous combination of NEB/RAM 5/2.5 mg versus patients uptitrated to the extemporaneous combination of NEB/RAM 5/5 mg or NEB/RAM 5/10 mg.

Number and proportion of patients achieving the standard BP goal (sitting SBP/DBP < 140/90 mmHg) at Visit 2 (Week 0), Visit 3 (Week 4), Visit 4 (Week 8) and Visit 5 (Week 12). Number and proportion of patients achieving the optimal BP goal (sitting BP < 130/80 mmHg in patients < 65 years old/sitting BP < 140/80 mmHg in patients  $\geq 65$  years old) at Visit 2 (Week 0), Visit 3 (Week 4), Visit 4 (Week 8) and Visit 5 (Week 12).

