• To evaluate the safety and tolerability of the monotherapies (NEB 5 mg and RAM 5 mg) and of the extemporaneous combinations (NEB/RAM 5/2.5 mg, NEB/RAM 5/5 mg, NEB/RAM 5/10 mg).	 Safety and tolerability of the monotherapies (NEB 5 mg and RAM 5 mg) and of the extemporaneous combination (NEB/RAM 5/2.5 mg, NEB/RAM 5/10 mg) measured by incidence, intensity (severity), seriousness of Adverse Events (AEs) during the study period, (screening, Run-in period and Assessment period), relationship to the study treatments, clinically significant abnormal change in vital signs, electrocardiogram (ECG), laboratory parameters and use of concomitant medications at Visit 2 (Week 0), Visit 3 (Week 4), Visit 4 (Week 8) and Visit 5 (Week 12). 	• Incidence of adverse drug reactions (ADRs), AEs, serious adverse events (SAEs), needs to be studied to address safety and tolerability of the extemporaneous combination.
Exploratory		
• To assess the antihypertensive efficacy of the extemporaneous combination of NEB 5 mg with RAM 2.5/5/10 mg by evaluating the patients who achieved the standard BP goal (sitting BP < 140/90 mmHg) at Visit 2 (Week 0), at Visit 3 (Week 4) and at Visit 4 (Week 8).	• Number and proportion of patients achieving the standard BP goal (sitting BP < 140/90 mmHg) at Visit 2 (Week 0), Visit 3 (Week 4) and Visit 4 (Week 8).	• The proportion of patients achieving the target is a very important clinical indicator of therapeutic success. ¹⁹
• To assess the antihypertensive efficacy of the extemporaneous combination of NEB 5 mg with RAM 2.5/5/10 mg by evaluating the patients who achieved the optimal BP goal (sitting BP < 130/80 mmHg in patients < 65 years	 Number and proportion of patients achieving the optimal BP goal (sitting BP < 130/80 mmHg in patients < 65 years old/sitting BP < 140/80 mmHg in patients ≥ 65 years old) at Visit 2 (Week 0), Visit 3 (Week 4), and Visit 4 (Week 8). 	• The proportion of patients achieving the target is a very important clinical indicator of therapeutic success. ¹⁹

MENARIN	Global Medical Department		
	Protocol Template		
Identification Number	Version Number State Effective date		
FORM-000050125	3.0, CURRENT	Effective	13 May, 2022

OBJECTIVES	ENDPOINTS	JUSTIFICATION FOR ENDPOINTS
old/sitting BP < 140/80 mmHg in patients ≥ 65 years old) at Visit 2 (Week 0), at Visit 3 (Week 4), and at Visit 4 (Week 8).		

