12.2 Determination of Sample Size

A sample size of 215 achieves 90% power to detect a Systolic BP difference of -2.4 mmHg between the null hypothesis mean of 3.0 mmHg and the alternative hypothesis mean of 5.4 mmHg with a known standard deviation of 12.0 mmHg and with a significance level (alpha) of 0.05 using a one-sided one-sample t-test. Such a difference in SBP is highly clinically significant in a population-wide perspective since, as clearly demonstrated by Hardy et al²⁰, if applied nationwide, a hypothetical 1 mmHg shift in SBP among African American and white US populations aged 45 to 64 years was estimated to prevent \approx 9338 incident heart failure events, 6210 incident coronary heart disease events, and 3761 incident stroke events annually, while the hypothetical intervention achieving the larger SBP reduction of 2 mmHg was associated with larger reductions in the incidence of coronary heart disease, stroke, and heart failure for both racial groups.

A total number of 270 patients will be screened considering a screen failure/drop-out rate of 20%, to obtain at least 215 completed patients at the EoS (Visit 5) (patients who complete all visits including EoS Visit [Visit 5]).

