12.5 Statistical Analysis

Descriptive statistics

Patient disposition, demographics and baseline characteristics will be summarized for monotherapy and combination therapy. Medical history will be summarized only for monotherapy. Prior and concomitant medications will be summarized for combination therapy (NEB + RAM).

Continuous variables will be summarized using the number of non-missing observations, mean, SD, minimum, median, and maximum values. Categorical variables will be presented with the number of non-missing observations and column percentages (n, %).

Primary (efficacy) analysis

The primary efficacy analysis will be conducted on the mITT population. The results will be interpreted for the same population.

The primary endpoint is the change in mean sitting SBP between Visit 2 (Week 0) and Visit 5 (Week 12).

The statistical hypothesis will be defined as below:

H0: There is no change in the sitting SBP post combination therapy.

H1: There is a difference in the sitting SBP post combination therapy.

The above hypothesis will be tested as following:

- Change from baseline in sitting SBP from prior and post combination therapy will be tested using paired t-test. The p-value obtained from the paired t-test will be presented.
- Assumption of Normality will be investigated using Wilk-Shapiro test. If the data is found to be non-Normal, the paired t-test will be replaced by Wilcoxon signed rank test.
- The primary endpoint will be summarized descriptively using n, mean, median, SD, Q1 (first quartile), Q3 (third quartile), minimum, and maximum.

MENARIN	Global Medical Department		
	Protocol Template		
Identification Number	Version Number	State	Effective date
FORM-000050125	3.0, CURRENT	Effective	13 May, 2022

Sensitivity analysis

The sensitivity analyses will be conducted using the PP population.

The PP population will be used to assess the robustness of the results obtained using the mITT population.

Secondary (efficacy) analysis

Secondary efficacy variables will be summarized in a descriptive manner using the mITT population.

- Change in mean sitting DBP between Visit 2 (Week 0) and Visit 5 (Week 12).
- Change in mean sitting DBP and SBP between:
 - Visit 2 (Week 0) and Visit 3 (Week 4)
 - Visit 2 (Week 0) and Visit 4 (Week 8)
- Number and proportion of patients achieving the standard BP goal (sitting BP < 140/90 mmHg) at Visit 5 (Week 12).

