## 7.4. Multiple Comparisons/ Multiplicity

Not Applicable.

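### SAP 16.2.1 lists exploratory goal rates and an undeclared dose-group comparison as secondary endpoints, against Protocol 4 and SAP 2.2/2.3

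*SAP*

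**What the plan says.** **Protocol.** Section 4 makes the standard and optimal goal rates secondary at Visit 5 only. The rates at the earlier visits are in the exploratory block: "Number and proportion of patients achieving the standard BP goal (sitting BP < 140/90 mmHg) at Visit 2 (Week 0), Visit 3 (Week 4", and likewise Visit 4 and the optimal goal. No endpoint compares dose groups. Section 12.5 introduces the secondary analysis with "Secondary efficacy variables will be summarized in a descriptive manner using the mITT population". It then gives two-sided 5% paired t-tests for the secondary BP changes, while the Visit 5 goal rates are summarised without a test. McNemar tests appear only in the exploratory part, for the optimal goal, between Visits 2 and 3, 2 and 4, and 3 and 4.

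**SAP, endpoint lists.** Sections 2.2 and 2.3 keep the protocol's classification.

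**SAP, analysis sections.** Section 16.2.1 lists as secondary both goal rates at Visits 2, 3, 4 and 5, and the change in systolic and diastolic BP (SBP, DBP) "in patients under extemporaneous combination of NEB/RAM 5/2.5 mg versus patients uptitrated to the extemporaneous combination of NEB/RAM 5/5 mg or NEB/RAM 5/10 mg". Sections 16.2.1.4 and 16.2.1.5 attach independent-samples t-tests; 16.2.1.6 and 16.2.1.7 attach McNemar tests. Section 16.2 adds: "Secondary efficacy variables will be analyzed using both the mITT as well as the PP population". Section 16.3.2 gives goal-rate McNemar tests again, as exploratory, on the enrolled and mITT populations.

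**SAP, governance.** Section 7.4 on multiplicity reads "Not Applicable". Section 3.3 on changes from plan reports only the exclusions at Sites 114 and 507.

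**The concern.** The SAP gives the same results two statuses. An author working from 2.2/2.3 would report the Visit 2 to 4 goal rates as exploratory; one working from 16.2.1 would report them as secondary efficacy, with p-values. The dose-group comparison has secondary status in 16.2.1 alone and no source in either endpoint list. Because 3.3 is silent, a reader of the study report could not tell that these items differ from the protocol.

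What is at stake is what may be called a secondary finding. The added tests are also poor candidates for that label: the dose groups are formed by the outcome, and optimal-goal attainment at Visit 2 is close to zero because controlled patients leave the study at that visit.

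**Working it through.** The documents state no count of secondary tests, so there is no figure of the plan's own to reproduce on this point.

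**1. Count per population.** Inputs are Protocol 12.5 and SAP 16.2.1.1 to 16.2.1.7. Four visits give 4 × 3 / 2 = 6 pairs per goal.

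| SAP section | Comparison | p-values | Protocol secondary | Protocol exploratory | New |
|---|---|---|---|---|---|
| 16.2.1.1 | SBP, DBP, Visit 2 to 3 | 2 | 2 | 0 | 0 |
| 16.2.1.2 | SBP, DBP, Visit 2 to 4 | 2 | 2 | 0 | 0 |
| 16.2.1.3 | DBP, Visit 2 to 5 | 1 | 1 | 0 | 0 |
| 16.2.1.4 | Dose groups, Visit 3 to 4, SBP and DBP | 2 | 0 | 0 | 2 |
| 16.2.1.5 | Dose groups, Visit 4 to 5, SBP and DBP | 2 | 0 | 0 | 2 |
| 16.2.1.6 | Standard goal, all visit pairs | 6 | 0 | 0 | 6 |
| 16.2.1.7 | Optimal goal, all visit pairs | 6 | 0 | 3 | 3 |
| Total | | 21 | 5 | 3 | 13 |

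Additions: 21 − 5 = 16, of which 3 are relabelled and 13 new. The 3 new optimal-goal tests all involve Visit 5.

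The six pairs rest on reading the comparison among Visits 3, 4 and 5 as three pairs, which 16.3.2 spells out. If it means two consecutive pairs, each goal has 5 tests and the total is 5 + 4 + 5 + 5 = 19. The count treats the Wilcoxon fallback as a replacement and leaves out the mixed-model covariate p-values.

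**2. One comparison, two methods.** For the standard goal against Visit 2:

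- SAP 16.2.1.6 (secondary): McNemar, exact only if a cell is zero.
- SAP 16.3.2 (exploratory): exact McNemar in every case.

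Both apply to mITT, so one comparison can have two statuses and two p-values.

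**3. What the dose-group tests compare.** At Visit 3 all patients are on 5/2.5 mg; uncontrolled patients move to 5/5 mg and controlled patients stay. SAP 16.2.1.4 then compares the change from Visit 3 to Visit 4. The Visit 3 reading therefore both assigns the group and is the baseline of the change.

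Suppose dose has no effect, and readings have mean μ, equal variance at both visits and correlation ρ < 1. The expected change given a Visit 3 reading x is

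E(change | x) = −(1 − ρ)(x − μ).

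Readings above μ are expected to fall and readings below it to rise, so the up-titrated group tends to show the larger fall without any dose effect. The documents give no ρ, so the size cannot be computed.

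The same holds at Visit 4 for patients on 5/5 mg who stay or move to 5/10 mg. SAP 16.2.1.5 does not say whether its 5/5 mg group includes patients raised to that dose at Visit 4. Its contrast of 5/5 with 5/10 mg also differs from the one listed in 16.2.1.

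**The case against.** **No multiplicity promise is broken.** There is one primary endpoint, and further secondary tests cannot inflate its error rate. The protocol calls its secondary analysis descriptive, sets its 5% tests in no order and controls no error rate. The lack of a protected place for the Week 12 DBP change is thus the protocol's choice, not a loss caused by the SAP. This stands.

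**A reader might infer a large false-positive rate.** Twenty-one independent tests with every null true would give 1 − 0.95^21 = 66%. The documents do not support that figure: the visit pairs overlap, SBP and DBP are correlated, and the optimal-goal tests against Visit 2 do not have a 5% false-positive rate when entry fixes the Visit 2 rate near zero.

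**A reader might double the count for the per-protocol repeat.** That set is nested in mITT, so the repeat is not 21 further chances. The population cell for secondary BP changes in Protocol 12.4 is also cut off in the available text. Section 12.5 says mITT, but a planned repeat for those changes cannot be ruled out.

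**A reader might infer that endpoints changed status after data were seen.** The trial is open-label, SAP v1.0 is dated 15 December 2023, first patient in was estimated by September 2023, and the v3.0 log of 17 April 2024 names 16.2.1. But the log does not say what changed there, the September date is an estimate, nothing shows that anyone looked at data, and Protocol 12.7 allows the SAP to be finalised up to database lock. The inference is not supported.

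**The duplicate may be drafting.** SAP 16.3.1 lists goal rates only within prior-therapy groups, so the McNemar tests in 16.3.2 may have been meant for those groups. As written, 16.3.2 does not limit them.

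None of this removes the conflict between 16.2.1 and 2.2/2.3, or the silence of 3.3.

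**Conclusion.** The point holds as a classification error and an undeclared addition. SAP 16.2.1 gives secondary status to exploratory goal rates and to a dose-group comparison found in no endpoint list. Per population, the secondary p-values go from 5 to 21, or 19 on the narrower reading. These are counts of p-values, not an error rate.

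The dose-group results should not be read as secondary evidence of efficacy or dose response. That conclusion follows from the titration rule and needs no numerical assumption beyond imperfect correlation between visits. The primary analysis is untouched.

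**What to change.** 1. In SAP 16.2.1, restore the SAP 2.2 list: the BP changes, and the goal rates at Visit 5 only, summarised as in Protocol 12.5.
2. Delete the goal-rate McNemar tests from 16.2.1.6 and 16.2.1.7. Keep them once in 16.3.2 with one stated method, and list the overall Visit 2 to 4 goal rates in 16.3.1.
3. Move the dose-group comparisons to 16.3 as exploratory and descriptive. Define the groups, and note that up-titration depends on BP at the visit from which the change is measured.
4. Record all additions in SAP 3.3.
5. In SAP 7.4, replace "Not Applicable" with a statement that only the primary test is confirmatory, that all secondary and exploratory p-values are nominal, and that per-protocol results are supportive.

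A fixed testing sequence is optional, needed only if the sponsor wants to claim significance for secondary endpoints.

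No new analysis is needed. The table shells, which SAP 4 ties to SAP approval and amendment, must be relabelled, and fewer results can be presented as secondary findings.

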# 16.2.1.1. CHANGE IN MEAN SITTING SBP AND DBP BETWEEN VISIT 2 (WEEK 0) AND VISIT 3 (Week 4)

Change from baseline in sitting SBP and DBP from prior and post combination therapy will be compared using paired t-test. The p-value will be presented using a paired t-test comparing mean at baseline and mean at Week 4. The secondary endpoint will be presented in a descriptive manner using n, mean, median, SD, Q1, Q3, and minimum and maximum. Assumption of normality will be investigated using Wilk-Shapiro test. If violation is observed, then paired t-test will be replaced by Wilcoxon signed rank test.

Additionally, the secondary end point of change in SBP and DBP between Visit 2 and Visit 3 will be analyzed using a repeated measures mixed model MMRM as described in Section Error! Reference source not found. with Age (Years), Gender, body mass index, and baseline BP (SBP or DBP) as covariates to identify the effect of covariates and interaction between the covariates.

# 16.2.1.2. CHANGE IN MEAN SITTING SBP AND DBP BETWEEN VISIT 2 (WEEK 0) AND VISIT 4 (Week 8)

Change from baseline in sitting SBP and DBP from prior and post combination therapy will be compared using paired t-test. The p-value will be presented using a paired t-test comparing mean at baseline and mean at Week 8. The secondary endpoint will be presented in a descriptive manner using n, mean, median, SD, Q1, Q3, and minimum and maximum. Assumption of normality will be investigated using Wilk-Shapiro test. If violation is observed, then paired t-test will be replaced by Wilcoxon signed rank test.

Additionally, the secondary end point of change in SBP between Visit 2 and Visit 4 will be analyzed using a repeated measures mixed model MMRM as described in Section Error! **Reference source not found.** with Age (Years), Gender, body mass index, and baseline BP (SBP or DBP) as covariates to identify the effect of covariates and interaction between the covariates.

Page 30 of 46

# 16.2.1.3. CHANGE IN MEAN SITTING DBP BETWEEN VISIT 2 (WEEK 0) AND VISIT 5 (WEEK 12)

Change from baseline in sitting DBP from prior and post combination therapy will be compared using paired t-test. The p-value will be presented using a paired t-test comparing mean at baseline and mean at Week 12. The secondary endpoint will be presented in a descriptive manner using n, mean, median, SD, Q1, Q3, and minimum and maximum. Assumption of normality will be investigated using Wilk-Shapiro test. If violation is observed, then paired t-test will be replaced by Wilcoxon signed rank test.

Additionally, the secondary end point of change in DBP between Visit 2 and Visit 5 will be analyzed using a repeated measures mixed model MMRM as described in Section 16.1.4 with Age (years), Gender, body mass index, and baseline DBP as covariates to identify the effect of covariates and interaction between the covariates.

# 16.2.1.4. CHANGE IN MEAN SITTING DBP AND SBP BETWEEN VISIT 3 (WEEK 4) AND VISIT 4 (WEEK 8)

Change in sitting SBP and DBP between patients under extemporaneous combination of NEB/RAM 5/2.5 mg versus patients uptitrated to the extemporaneous combination of NEB/RAM 5/5 mg will be compared using independent samples t-test. The secondary endpoint will be presented in a descriptive manner using n, mean, median, SD, Q1, Q3, and minimum and maximum. Assumption of normality will be investigated using Wilk-Shapiro test. If the data is found to be non-Normal, the independent samples t-test will be replaced by Wilcoxon rank-sum test.

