c. Patients on NEB 5 mg or RAM 5 mg will continue the same therapy for 4 weeks (Run-in period), while patients on any other BBs will be assigned to monotherapy with NEB 5 mg and patients on other ACE-is will be assigned to monotherapy with RAM 5 mg.

AENARIN		Glot	bal Medical Department
	Protocol Template		
Identification Number	Version Number State Effective date		Effective date
FORM-000050125	3.0, CURRENT	Effective	13 May, 2022

Sponsor: Menarini International Operations Luxembourg SA	Protocol Version_3.0 of 13/07/2023
Study Code: MEIN/22/NeRam-Hyp/001	

- d. Only patients with uncontrolled BP at Visit 2 will receive NEB/RAM 5/2.5 mg for next 4 weeks, while patients with controlled BP levels will be withdrawn from the study.
- e. Only patients with uncontrolled BP at Visit 3 will be up-titrated from NEB/RAM 5/2.5 mg to NEB/RAM 5/5 mg for next 4 weeks, while patients with controlled BP levels will continue the same extemporaneous combination.
- f. Only patients with uncontrolled BP at Visit 4 will be up-titrated if on NEB/RAM 5/2.5 mg to NEB/RAM 5/5 mg and if on NEB/RAM 5/5 mg to NEB/RAM 5/10 mg for next 4 weeks, while patients with controlled BP levels will continue the same extemporaneous combination as Visit 3.
- g. All concomitant medications ongoing at the time of the consent and any surgery/procedures should be reported.
- h. Pregnancy test (urine) is only for female patients of childbearing potential.
- i. Vital signs will include body temperature, respiratory rate, sitting BP, and pulse rate.
- j. To ensure patient safety, the patients will be contacted over a phone call within 24 hours, in case of any abnormality and clinically relevant laboratory test according to the Investigator's judgment at any visit.
- k. Patients having any ongoing AE/SAE at the end of the treatment will be followed for further 2 weeks via a phone call to check about the status of the AE/SAE.
- 1. These procedures are referred to the COVID-19 Appendix (Appendix 2).

MENARINI	Global Medical Department		
	Protocol Template		
Identification Number	Version Number	State	Effective date
FORM-000050125	3.0, CURRENT	Effective	13 May, 2022
Enclosure to: 🗆 Guideline	□ Policy x I	Procedure D	Working Instruction

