Patients with uncontrolled BP levels (sitting BP \geq 130/80 mmHg in patients < 65 years old/sitting BP \geq 140/80 mmHg in patients \geq 65 years old) at Visit 2, with adequate treatment adherence (ranging between 80% to 120%) and who did tolerate the treatment, will enter into the Assessment period and will be assigned to the extemporaneous combination of NEB/RAM 5/2.5 mg. Patients with controlled BP levels (sitting BP < 130/80 mmHg in patients < 65 years old/sitting BP < 140/80 mmHg in patients \geq 65 years old) and/or who do not tolerate the treatment or have an adherence range below 80% or above 120%, will be withdrawn from the study (drop-out patients).

CONFIDENTIAL

MENARINI	Global Medical Department		
	Protocol Template		
Identification Number	Version Number	State	Effective date
FORM-000050125	3.0, CURRENT	Effective	13 May, 2022

After 4 weeks \pm 2 days in the Assessment period (Week 4), patients BP will be further evaluated at Visit 3: patients with controlled BP levels (sitting BP < 130/80 mmHg in patients < 65 years old/sitting BP < 140/80 mmHg in patients \geq 65 years old) will continue the same extemporaneous combination, while patients with uncontrolled BP levels (sitting BP \geq 130/80 mmHg in patients < 65 years old/sitting BP \geq 140/80 mmHg in patients \geq 65 years old) will be up-titrated from NEB/RAM 5/2.5 mg to NEB/RAM 5/5 mg for further 4 weeks \pm 2 days.

After further 4 weeks \pm 2 days (Week 8) the BP will be assessed again (Visit 4): controlled patients will continue the same extemporaneous combination, while uncontrolled patients:

- if on NEB/RAM 5/2.5 mg, will be up-titrated to NEB/RAM 5/5 mg for further 4 weeks ± 2 days (Visit 5, Week 12);
- if on NEB/RAM 5/5 mg, will be up-titrated to NEB/RAM 5/10 mg for further 4 weeks ± 2 days (Visit 5, Week 12).

At the end of the Assessment period (12 weeks \pm 2 days), at Visit 5, the antihypertensive effect of the extemporaneous combination (NEB/RAM 5/2.5 mg, NEB/RAM 5/5 mg or NEB/RAM 5/10 mg) will be evaluated.

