## Assessment period from Visit 2 (Week 0) to Visit 5 (Week 12):

After 4 weeks (± 2 days) of the Run-in period of monotherapy (Week 0), BP will be further assessed at Visit 2.

Patients with uncontrolled BP levels (sitting BP  $\geq$  130/80 mmHg in patients < 65 years old/sitting BP  $\geq$  140/80 mmHg in patients  $\geq$  65 years old) at Visit 2, with adequate treatment adherence (ranging between 80% to 120%) and who did tolerate the treatment, will enter into the Assessment period and will be assigned to the extemporaneous combination of NEB/RAM 5/2.5 mg. Patients with controlled BP levels (sitting BP < 130/80 mmHg in patients < 65 years old/sitting BP < 140/80 mmHg in patients  $\geq$  65 years old) and/or who do not tolerate the treatment or have an adherence range below 80% or above 120%, will be withdrawn from the study (drop-out patients).

After 4 weeks  $\pm 2$  days in the Assessment period (Week 4), patients BP will be further evaluated at Visit 3:

[figure not shown]
patients with controlled BP levels (sitting BP < 130/80 mmHg in patients < 65 years old/sitting BP < 140/80 mmHg in patients  $\geq$  65 years old)) will continue the same extemporaneous combination, while patients with uncontrolled BP levels will be up-titrated from NEB/RAM 5/2.5 mg to NEB/RAM 5/5 mg for further 4 weeks  $\pm$  2 days.

After further 4 weeks  $\pm$  2 days (Week 8) the BP will be assessed again (Visit 4): controlled patients will continue the same extemporaneous combination, while uncontrolled patients:if on NEB/RAM 5/2.5 mg, will be up-titrated to NEB/RAM 5/5 mg for further 4 weeks  $\pm$  2 days (Visit 5, Week 12);

if on NEB/RAM 5/5 mg, will be up-titrated to NEB/RAM 5/10 mg for further 4 weeks  $\pm$  2 days (Visit 5, Week 12).

At the end of the Assessment period (12 weeks  $\pm$  2 days), at Visit 5, the antihypertensive effect of the extemporaneous combination (NEB/RAM 5/2.5 mg, NEB/RAM 5/5 mg or NEB/RAM 5/10 mg) will be evaluated.

To correctly evaluate the additional effect of the combination therapy, the number of patients with uncontrolled BP on NEB or RAM monotherapy needs to be balanced at Visit 2. To maintain a 1:1 ratio during the Assessment period, a cap of 110 patients for each treatment arm

Page 15 of 46

(i.e., NEB and RAM) will be included at Visit 2 to maintain a balanced number of uncontrolled patients entering the Assessment period for each drug.

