#### 6.6. Common Calculations

For quantitative measurements, change from baseline will be calculated as:

• Test Value at Visit X – Baseline Value

And for change between Visit 3 and Visit 4 will be calculated as:

• Test Value at Visit 4 – Visit 3 Value

And for change between Visit 4 and Visit 5 will be calculated as:

• Test Value at Visit 5– Visit 4 Value

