# 16.2.1.5. CHANGE IN MEAN SITTING DBP AND SBP BETWEEN VISIT 4 (WEEK 8) AND VISIT 5 (WEEK 12)

Change in sitting SBP and DBP between patients under extemporaneous combination of NEB/RAM 5/5 mg versus patients uptitrated to the extemporaneous combination of NEB/RAM 5/10 mg will be compared using independent samples t-test. The secondary endpoint will be presented in a descriptive manner using n, mean, median, SD, Q1, Q3, and minimum and maximum. Assumption of normality will be investigated using Wilk-Shapiro test. If the data is found to be non-Normal, the independent samples t-test will be replaced by Wilcoxon rank-sum test.

16.2.1.6. Number and proportion of patients achieving the BP goal (sitting BP < 140/90 mmHg) will be summarized for Visit 2 (Week 0), Visit 3 (Week 4), Visit 4 (Week 8) and Visit 5 (Week 12) along with percentage and 95% CI (Clopper Pearson). A p-value using McNemar's test, or exact McNemar's test proposed when one of the cell frequency is 0, will be presented to compare the proportion of patients achieving the Standard BP goal (sitting BP < 140/90 mmHg) between Visit 2 and Visit 3, Visit 2 and Visit 4, Visit 2 and Visit 5, and, as well as, between Visit 3, Visit 4 and Visit 5.

Page 31 of 46

16.2.1.7. Number and proportion of patients achieving the optimal BP goal(sitting BP < 130/80 mmHg in patients < 65 years old/sitting BP < 140/80 mmHg in patients  $\geq 65$  years old)

The number of patients achieving the BP goal (sitting BP < 130/80 mmHg in patients < 65 years old/sitting BP < 140/80 mmHg in patients  $\geq$  65 years old) will be summarized for Visit 2 (Week 0), Visit 3 (Week 4), Visit 4 (Week 8) and Visit 5 (Week 12) along with percentage and 95% CI (Clopper Pearson). A p-value using exact McNemar's test will be presented to compare the proportion of patients achieving the BP goal (sitting BP < 130/80 mmHg in patients < 65 years old/sitting BP < 140/80 mmHg in patients  $\geq$  65 years old) between Visit 2 and Visit 3, as well as Visit 2 and Visit 4 as well as Visit 2 and Visit 5. A p-value using McNemar's test will be presented to compare the proportion of patients achieving the BP goal (sitting BP < 130/80 mmHg) between Visit 3, Visit 4 and Visit 5.

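### The dose-step tests in SAP 16.2.1.4 and 16.2.1.5 compare groups formed by the very reading they subtract, and the optimal-goal McNemar tests use a Visit 2 rate that the entry rule sets to 0%

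*SAP*

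**What the plan says.** **Dose groups.** Everyone entering the Assessment period takes NEB/RAM 5/2.5 mg until Visit 3. Controlled patients then stay on that dose, "while patients with uncontrolled BP levels will be up-titrated from NEB/RAM 5/2.5 mg to NEB/RAM 5/5 mg" (SAP 3.1; Protocol 2.2, notes e and f). At Visit 4 the same rule moves uncontrolled patients from 5/2.5 to 5/5, or from 5/5 to 5/10.

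**Outcome.** SAP 6.6 says "And for change between Visit 3 and Visit 4 will be calculated as" the Visit 4 value minus the Visit 3 value, and defines Visit 4 to Visit 5 in the same way.

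**Tests between doses.** SAP 16.2.1.4 compares patients on 5/2.5 "versus patients uptitrated to the extemporaneous combination of NEB/RAM 5/5 mg will be compared using independent samples t-test". SAP 16.2.1.5 compares patients on 5/5 "versus patients uptitrated to the extemporaneous combination of NEB/RAM 5/10 mg will be compared using independent samples t-test". Both switch to the rank-sum test if normality fails, and neither adjusts for the starting value. SAP 16.2.1 describes another contrast: 5/2.5 "versus patients uptitrated to the extemporaneous combination of NEB/RAM 5/5 mg or NEB/RAM 5/10 mg".

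**Optimal goal.** At Visit 2, uncontrolled patients go on to the combination, "while patients with controlled BP levels will be withdrawn from the study" (Protocol 2.2, note d). Protocol section 5 agrees: controlled patients "will be withdrawn from the study (drop-out patients"). The cut-offs for control are the age-specific cut-offs of the optimal goal. SAP 16.2.1.7 nevertheless tests that goal by exact McNemar "between Visit 2 and Visit 3, as well as Visit 2 and Visit 4 as well as Visit 2 and Visit 5", and SAP 16.3.2 does so again. Protocol 12.5 plans the Visit 2 versus Visit 3 and Visit 2 versus Visit 4 tests as exploratory.

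**The concern.** In the dose-step tests one reading does two jobs: it assigns the group and it is the start value of the change. Patients selected because a reading was high tend to read lower next time, and patients selected because it was low tend to read higher. The up-titrated group therefore shows the larger fall even if the extra dose does nothing. The rank-sum test has the same fault.

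In the optimal-goal tests, a patient who starts the combination under the entry rule cannot be at goal at Visit 2 and lose it later. One discordant cell is empty by design, so any later achievers, including those produced by visit-to-visit noise, count in one direction.

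The study report could then carry a small p-value for 5/5 over 5/2.5 that reads as dose-response evidence, and optimal-goal p-values that can be small without a drug effect. The SAP labels the dose-step tests secondary, but they serve no objective in SAP 2.2, are absent from Protocol 12.5, and are not listed in SAP 3.3 as a change.

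**Working it through.** **Inputs from the documents.** N = 215, SD 12.0 mmHg, detectable SBP difference 2.4 mmHg (Protocol 12.2); two-sided 5% tests (SAP 6.5); the titration, change and entry rules above. The documents give no between-visit correlation and no share of uncontrolled patients, so these are assumed and varied.

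**1. The plan's own figure.** n = [(1.645 + 1.282) × 12/2.4]² = 214.1 with unrounded z values, so 215. This reproduces. The documents give no figure for the tests at issue; 2.4 mmHg serves as a yardstick.

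**2. Closed form, Visit 3 to Visit 4, SBP only, no dose effect.** Let ρ be the between-visit correlation, p the share uncontrolled, φ the standard normal density at the cut-off, and SD = 12/√(2(1−ρ)). The extra fall in the up-titrated group is (1−ρ) × SD × [φ/p + φ/(1−p)].
- ρ = 0.5, p = 0.5: SD = 12.0; 0.5 × 12.0 × (0.399/0.5 + 0.399/0.5) = 9.6 mmHg.
- ρ = 0.8, p = 0.5: SD = 19.0; 0.2 × 19.0 × 1.596 = 6.1 mmHg.
- Over ρ 0.5 to 0.8 and p 0.3 to 0.7 the range is 6.1 to 9.9 mmHg. In 1,500 simulated null trials per setting the t-test was significant in 94 to 100%.

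**3. Simulation closer to the trial.** 2,000 trials of 215 patients in each of eight settings, with uncontrolled meaning SBP or DBP at or above its limit. Assumed:
- mean on monotherapy 140/84 or 145/88 mmHg before selection;
- between-patient SBP SD 10 or 15, and visit-noise SBP SD 5.7 or 8.5 (8.5 = 12/√2 treats the whole planning SD as noise, so it is the high end);
- DBP SDs 0.6 times (between) and 0.65 times (noise) those of SBP, correlation 0.5;
- 40% aged 65 or older;
- true BP constant from Visit 3, at 5.4/3.0 mmHg below monotherapy (5.4 is the plan's alternative).

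| Comparison, no dose-step effect | False difference (mmHg) | t-test significant |
|---|---|---|
| Visit 3 to 4, SBP | 5.7–10.0 | 55–99% (rank-sum 54–98%) |
| Visit 3 to 4, DBP | 3.3–6.9 | 48–98% |
| Visit 4 to 5, SBP, 5/5 = stayers only | – | 54–96% |
| Visit 4 to 5, SBP, 5/5 includes those just moved up | – | 21–50% |

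On average 9 to 31 of the 215 stay on 5/2.5 at Visit 3. With a fall of 8/5 mmHg instead (1,000 trials), the Visit 3 to 4 SBP figures are 5.1 to 9.2 mmHg and 69% to over 99%.

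**4. Optimal goal against Visit 2.** With one discordant cell empty, exact McNemar gives p = 2 × 0.5^c for c later achievers. c = 5 gives 0.0625; c = 6 gives 0.031, and 6/215 = 2.8%. With no drug effect (1,000 trials per setting), 1.1 to 6.0% are at goal at Visit 5 by chance, and the test rejects in 4 to 99% of trials, driven mainly by visit noise and mean BP. The standard-goal test rejects in 3 to 15%: a patient under 65 at 135/85 can enter already below 140/90, so that Visit 2 rate is not fixed.

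**5. Wording.** The Visit 3 to 5 sentence in SAP 16.2.1.7 and the optimal-goal McNemar sentences in SAP 16.3.2 give only 130/80. The same subsections define the goal with a separate 140/80 limit from age 65.

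**The case against.** **The 0% is not universal.** SAP 16.3.2 also uses the ENR population, which holds patients withdrawn as controlled at Visit 2, and early leavers are asked to complete the Visit 5 assessments. The ENR Visit 2 summary rate can indeed exceed 0%. The paired tests change little: withdrawn patients have no Visit 3 or Visit 4, and the SAP reports by nominal visit (6.3) with a separate early-termination label (Appendix 1). Two-way discordance could arise in ENR only if a withdrawal assessment were analysed as Visit 5.

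**The planners foresaw the zero.** Protocol 12.5 switches to the exact test when a visit has no achievers. That settles the computation, not what the p-value means.

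**The sizes rest on assumptions.** This stands. The McNemar range of 4 to 99% runs from no inflation to near certainty, and the dose-step percentages shift with the assumed variances. The direction of the dose-step bias does not shift, and its smallest SBP value for Visit 3 to 4 in step 3 (5.7 mmHg) is more than twice the planned 2.4 mmHg.

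**These are not primary tests, and part is editorial.** The primary paired t-test is untouched, the descriptive summaries and Clopper-Pearson intervals are already planned, and the missing age limit may be leftover text. All true. It makes the repair cheap, but leaves the p-values in the report.

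**Conclusion.** The concern holds and should be fixed. The dose-step tests in SAP 16.2.1.4 and 16.2.1.5 are biased toward up-titration by the titration rule itself. For Visit 3 to 4 SBP the false difference is 5.7 to 10.0 mmHg and 55 to 99% of null trials are significant, under the assumed means and variances; the direction needs no such assumption. For Visit 4 to 5 the size also depends on a group definition that the SAP does not give.

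The optimal-goal McNemar tests against Visit 2 do not measure a drug effect among patients who start the combination. How often they would mislead cannot be fixed from the documents. McNemar comparisons among Visits 3 to 5 are not affected by the entry rule, the standard-goal tests are affected much less, and the primary conclusion does not depend on any of this.

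**What to change.** - **SAP 16.2.1.4 and 16.2.1.5:** delete the between-group p-values and report change by dose path descriptively. State whether the 5/5 group includes patients moved up from 5/2.5 at Visit 4, and align the contrast in SAP 16.2.1.
- **If a dose-step estimate is wanted:** label it exploratory and model next-visit BP adjusted for the triggering SBP and DBP and for age group. State that the groups barely overlap on the starting reading, so the estimate leans on linearity. In the step 3 simulation this model still rejected in 6 to 14% of null trials with a bias of 0.7 to 2.2 mmHg, so it should not carry a claim. (An SBP-only rule gave 4 to 6%, which is too favourable a picture.)
- **SAP 16.2.1.7 and 16.3.2:** delete the optimal-goal McNemar p-values against Visit 2 and report the proportion at each later visit with its 95% CI. Keep the standard-goal tests, noting that patients were selected on BP at Visit 2. Use the age-specific goal in every optimal-goal comparison.
- **SAP 3.3:** record the departure from Protocol 12.5, which prescribes the optimal-goal p-values for Visit 2 against Visits 3 and 4.

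The cost is a SAP amendment and revised table shells. No new data are needed and the primary analysis is unchanged. The sponsor gives up only p-values that the selection rules make uninterpretable.
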